2.2 Screening

Screening will take place 3-11 weeks post-injury. After signing the informed consent form, inclusion/exclusion criteria, concomitant medications, and medical history will be reviewed and demographic information will be collected. Subject will have a physical examination, including height and weight. Vital signs (systolic blood pressure, diastolic blood pressure, and heart rate) will be recorded. Samples will be collected for hematology/chemistry (with HbA1c)/urinalysis and prostate specific antigen (PSA, males only). A Mini Mental State Exam will be performed on all subjects to verify cognitive function. The 4-meter walk test will also be performed to verify ambulatory ability. A 12-lead ECG will be used to verify cardiac function. Pre-fracture physical and instrumental activities of daily living (PADLs/IADLs) will be conducted by subject interview. Baseline DXA scans will be scheduled at this time.

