2.3 Randomization/Baseline

Approximately 1 week (± 2 days) after Screening (4-12 weeks post-injury), subjects will be expected to arrive at the clinic following a minimum 10-hour fast. They will be allowed to have a light snack after all bloodwork is complete.

Baseline procedures will include:

- Review concomitant medications
- Vital signs (systolic blood pressure, diastolic blood pressure, and heart rate)
- Hematology/Chemistry/Urinalysis
- Bone Turnover Markers
- Vitamin D
- Thyroid Markers
- Fasting Lipid Profile
- Coagulation
- Pituitary/Adrenal Hormone Blood Tests
- Pancreatic Endocrine Markers
- Dual-Energy X-Ray Absorptiometry (DXA) Scans
- 12-Lead ECG at 2 hours post-dose
- Six-Minute Walk Test (6MWT) and BORG Scale, Grip Strength, and Short Physical Performance Battery (SPPB)
- Post-fracture PADLs/IADLs
- Short Form-36 (SF-36)

Subjects will be randomized to one of four treatment arms (VK5211 0.5 mg, 1.0 mg, 2.0 mg, or placebo) in a 1:1:1:1 ratio and will receive their first dose of study treatment in the clinic. Adverse events will be recorded. A bottle of study treatment (30 capsules) will be dispensed and subjects will be instructed to take one oral dose of the assigned treatment at approximately the same time every morning, 30 minutes prior to breakfast. Subjects will be informed that they may have more doses than they will need and must return any extra study treatment at Visit 2. They will receive a diary card to record their treatment administration and meal and snack times for 3 days prior to Visit 2.

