2.10 Schedule of Events

[Table 1](#) below describes the schedule of events for all study visits.

Table 1. Schedule of Events for All Study Visits

Visit	Screening	Randomization /Baseline	Visit 1 TC	Visit 2	Visit 3	Visit 4	Visit 5	Early Term
Days	-7 ± 2 days	0	7(-5/+2)	28(-5/+2)	56(-5/+2)	84(-5/+2)	168 ± 5	
Informed Consent	X							
Medical History	X							
Demographics	X							
Inclusion/Exclusion Criteria	X							
Mini Mental State Exam	X							
4-Meter Walk Test	X							
Concomitant Medications	X	X	X	X	X	X	X	X
Physical Exam ¹	X			X		X	X	X
Vital Signs	X	X		X	X	X	X	X
ECG ²	X	X ²				X ²	X	X
Hematology/Chemistry/Urinalysis ^{12,13}	X ¹²	X		X	X ¹³	X	X ¹³	X
Lipid Profile		X		X		X	X	X
Coagulation		X		X		X	X	X
Thyroid Markers ³		X				X		X
Vitamin D		X				X		X
Bone Turnover Markers ⁴		X		X	X	X	X	X
Pituitary/Adrenal Hormone Blood Tests ⁵		X		X		X		X
PSA (males)	X					X		X
Pancreatic Endocrine Markers ⁶		X		X	X	X		X
DXA Scan		X				X	X	X
Physical Performance Assessments ⁷		X		X	X	X	X	X
Patient Reported Outcomes ⁸	X (pre-Fx. Only)	X		X	X	X	X	X
Plasma Concentration Blood Samples ⁹				X ⁹	X ⁹	X ⁹	X ⁹	
Diary Card ¹⁰		X		X	X	X		
IP Administration/Dispensation/Compliance ¹¹		X	X	X	X	X		X
Averse Events		X	X	X	X	X	X	X
Study Disposition							X	X

¹ Height and weight will be measured at Screening. Weight only at Visits 2, 4, and 5.

² At Randomization and at Visit 4, the ECG will occur at 2 hours post-dose.

³T3, T4, TSH

⁴ s-CTX and s-PINP

⁵ The hormones tested will include follicle stimulating hormone (FSH), luteinizing hormone (LH), sex-hormone binding globulin (SHBG), estradiol, cortisol, aldosterone, adrenocorticotrophic hormone (ACTH) and total and free testosterone.

⁶ Endocrine pancreatic markers include fasting insulin and fasting glucagon

⁷ 6MWT and BORG Scale, Grip Strength, and SPPB.

⁸ Pre-fracture PADLs/IADLs at Screening. SF-36 and post-fracture PADLs/IADLs at Randomization. Post-fracture PADLs/IADLs only at Visits 2 and 3. SF-36 and post-fracture PADLs/IADLs at Visits 4 and 5 and Early Termination.

⁹Samples will be drawn pre-dose and at 2 hours (± 10 min) post-dose at Visits 2, 3, and 4. Visit 5 sample may be drawn along with the other blood work samples.

¹⁰ Diary cards provided at Randomization and Visit 3, reviewed at Visits 2 and 4.

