6.9.2 Physical and Instrumental Activities of Daily Living (PADLs/IADLs)

PADLs/IADLs will be conducted by subject interview at Screening, Randomization, Visits, 2, 3, 4, and 5 and in case of early withdrawal as shown in [Table 1](#). At Screening, only the pre-fracture PADLs/IADLs will be conducted by subject interview. At all other visits, only the post-fracture PADLs/IADLs will be conducted. The pre-fracture PADLs/IADLs questionnaire is provided in [Appendix 15.6](#); the post-fracture PADLs/IADLs questionnaire is provided in [Appendix 15.7](#).

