2.3. Definition of Baseline

In general, the study baseline is defined as the last observation obtained prior to the administration of the first randomized study medication, unless otherwise specified.

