2.10.3.2. Patient Reported Outcomes

2.10.3.2.1. Pre- and Post-Fracture Physical and Instrumental Activities of Daily Living

For the analysis of the PADLs/IADLs, entirely dependent means that the subject is unable to perform the activities without assistance. For Example:

- The IADL Q1 discusses how the subject got to places out of walking distance.
 - Responses that would not be entirely dependent are:
 - Response 1 (Travel alone on buses, taxis, or drive your own car)
 - Response 3 or 4 (Did not perform), if Q1a has a response of 1 (Independently)
 - Responses that would be entirely dependent are:
 - Response 2 (Have someone to help you or go with you when travelling)
 - Response 3 or 4 (Did not perform), if Q1a has a response of 2 (With Assistance) or 3 (Would not be able to at all).

A significant change from screening would be a change in the subjects entirely dependent rating. A significant positive change would be if someone was entirely dependent at screening, but independent at the post-baseline visit. A significant negative change would be if someone was independent at screening, but entirely dependent at the post-baseline visit.

The PADLs/IADLs will be analyzed as follows:

- Change in number of subjects entirely dependent in performing each activity of daily living from screening at each post-screening visit will be analyzed using the Cochran-Mantel-Haenszel Test.
- Difference in number of subjects entirely dependent in performing each activity of daily living at each visit between treatment groups will be compared using the Cochran-Mantel-Haenszel Test.
- Each activity of daily living for each visit collected will be summarized using mean, standard deviation, median, minimum and maximum.
- Significant change from screening for each activity of daily living will be analyzed using the Wilcoxon signed-rank test.

- Differences between treatment groups for each activity of daily living will be analyzed using the Kruskal-Wallis test on the change from screening value.

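### Neither between-arm ADL test in the SAP adjusts for the post-fracture status recorded at Randomization, which costs precision in an exploratory comparison

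*SAP*

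**What the plan says.** The ADL questionnaires come in two versions. Protocol 6.9.2 assigns them by visit: "At Screening, only the pre-fracture PADLs/IADLs will be conducted by subject interview". It continues: "At all other visits, only the post-fracture PADLs/IADLs will be conducted". The footnotes to the Schedule of Events (Protocol 2.10) confirm that the second version is given before treatment: "SF-36 and post-fracture PADLs/IADLs at Randomization".

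The Screening value is therefore a recollection. Protocol 2.2 states: "Screening will take place 3-11 weeks post-injury". The questions in Appendix 15.6 concern the one week (physical items) or two weeks (instrumental items) before the fracture. The Randomization value concerns the past one or two weeks (Appendix 15.7), in subjects then 4-12 weeks after injury (Protocol 2.3).

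SAP 2.10.3.2.1 plans two comparisons between arms:

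- For item scores: "Differences between treatment groups for each activity of daily living will be analyzed using the Kruskal-Wallis test on the change from screening value".
- For the number of subjects entirely dependent, groups "at each visit between treatment groups will be compared using the Cochran-Mantel-Haenszel Test". No stratification variable is named.

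The Wilcoxon signed-rank test, a further CMH test and the definition of a significant change are also anchored to screening. Protocol 9.3.3 lists the same tests.

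Elsewhere in the SAP, "the study baseline is defined as the last observation obtained prior to the administration of the first randomized study medication" (SAP 2.3), subject to exceptions specified in place. Baseline is a covariate in the analyses of DXA measures (2.10.1, 2.10.2.1), six-minute walk and Borg scale (2.10.3.1.1), grip strength (2.10.3.1.2), mean SPPB (2.10.3.1.3) and SF-36 (2.10.3.2.2).

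**The concern.** The exploratory objective is efficacy against placebo after 12 weeks of treatment. Subjects enter over an eight-week span of recovery, so function at Randomization is likely to vary widely for reasons unrelated to treatment. A measurement of that function is already in the database, and using it would remove some of the variation from the comparison. Subtracting recalled pre-fracture status does not do this, and it may add noise of its own.

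The change-from-screening score also blurs what happened on treatment. A subject who was independent before the fracture, dependent at Randomization and independent at Week 12 scores no change. So does a subject who was independent throughout.

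At stake is the ability of the ADL comparison to show a treatment effect with about 23 completers per arm (SAP 2.14).

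**Working it through.** **Figures in the documents.** There is no ADL power, SD or correlation to reproduce. The only power figures are for lean body mass. With 30 per arm, a difference of 1.0 kg and SD 1.3, normal-approximation power is Φ(1.0/(1.3·√(2/30)) − 1.96) = Φ(1.02) ≈ 84.6%, against the stated 84%. That figure reproduces but has no bearing on the ADL items. Everything below rests on assumed inputs and shows direction and plausible range only.

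**Variance formulas.** Work in units of the Week 12 variance. Let k be the pre-fracture SD divided by the Week 12 SD, and take the Randomization SD as equal to the Week 12 SD. Let r_pre and r_rand be the correlations of the Week 12 value with the pre-fracture and Randomization values.

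- Change from pre-fracture: 1 + k² − 2·k·r_pre
- Simple change from Randomization: 2(1 − r_rand)
- Adjustment for the Randomization value (ANCOVA): 1 − r_rand²

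| k | r_pre | r_rand | Change from pre-fracture | Change from Randomization | Adjusted | Pre-fracture / adjusted |
|---|---|---|---|---|---|---|
| 0.5 | 0.3 | 0.4 | 0.95 | 1.20 | 0.84 | 1.13 |
| 0.5 | 0.3 | 0.6 | 0.95 | 0.80 | 0.64 | 1.48 |
| 1.0 | 0.3 | 0.6 | 1.40 | 0.80 | 0.64 | 2.19 |
| 1.0 | 0.3 | 0.8 | 1.40 | 0.40 | 0.36 | 3.89 |
| 0.5 | 0.5 | 0.5 | 0.75 | 1.00 | 0.75 | 1.00 |

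Over k = 0.5-1.0, r_pre = 0.3-0.5 and r_rand = 0.4-0.8 (r_rand not below r_pre), the last ratio runs from 1.00 to 3.89. There is no loss in the bottom row. In the first and last rows, simple change from Randomization has a larger variance than the planned score.

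**Simulation of the item-score test.** These formulas treat the scores as continuous, whereas the planned test uses ranks. A simulation therefore used a five-level item in four arms, with a latent effect rising in equal steps to 0.8 SD at the top dose (2,000 trials per setting). Power:

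| n per arm | r_pre | r_rand | Planned: change from pre-fracture | Simple change from Randomization | Visit value alone | Rank test adjusted for Randomization |
|---|---|---|---|---|---|---|
| 23 | 0.3 | 0.4 | 39% | 28% | 51% | 53% |
| 23 | 0.3 | 0.6 | 40% | 36% | 51% | 62% |
| 23 | 0.3 | 0.8 | 38% | 53% | 49% | 76% |
| 23 | 0.5 | 0.5 | 46% | 33% | 49% | 55% |
| 30 | 0.3 | 0.4 | 51% | 36% | 65% | 67% |
| 30 | 0.3 | 0.6 | 50% | 48% | 64% | 74% |
| 30 | 0.3 | 0.8 | 49% | 67% | 64% | 87% |

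Type I error was 0.035 to 0.060 for all four methods. The gain has two sources. With 23 per arm and r_pre 0.3, dropping the subtraction of pre-fracture status gives 11 to 12 points. Adjustment then adds about 2, 11 and 27 points as r_rand rises from 0.4 to 0.8.

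**Simulation of the dependence test.** With 23 per arm, again on assumed inputs, stratifying the between-arm CMH test by dependence at Randomization raised power from about 50% to 52-62%, with type I error near 5%. This gain is smaller because the CMH test already uses current status and the stratum is only a yes/no split.

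**The case against.** The plan has a substantial defence.

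- **The reference is deliberate and permitted.** SAP 2.3 allows exceptions, the ADL section specifies screening, Protocol 9.3.3 set out the same tests, and the objective names both pre- and post-fracture ADLs. Return to pre-fracture function is a legitimate question. This stands, and it is why the change-from-screening analyses should stay.
- **Little depends on it.** ADLs are exploratory and are absent from the variables listed for the primary analysis (SAP 2.11). The other functional measures already adjust for baseline. This stands too.
- **The loss may be nil.** If recalled pre-fracture status predicts Week 12 as well as the Randomization value does and has half the SD, the formula shows no loss against adjustment. This is possible, but the documents do not say which case applies.

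A reader might infer more than the documents support:

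- *That every ADL treatment comparison is a change from recalled status.* The by-visit CMH test compares current status.
- *That the Randomization value is discarded.* As written, it enters the by-visit summaries, the by-visit CMH test and the post-screening change results as a visit. Only its use as baseline or covariate is missing.
- *That the comparison is biased, or could routinely mimic a drug effect.* Allocation is randomized and simulated type I error stayed near 5%.
- *That changing the reference to Randomization would be enough.* Simple change from Randomization had less power than the planned test at r_rand of 0.6 or below in the simulation.

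Protocol 7.3 does not fix whether the Randomization interview precedes the first dose. Because the questions look back one or two weeks, the value describes essentially the pre-dose state either way.

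**Conclusion.** The point holds as a precision weakness in an exploratory analysis. Neither between-arm ADL test uses the post-fracture Randomization value as baseline, covariate or stratum, and the SAP gives no reason for treating ADLs differently from its other functional and patient-reported outcomes. The tests remain valid.

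The size of the loss cannot be established from the documents. Over the simulated settings, adjustment gained between about 9 points (23 per arm, both correlations 0.5) and 38 points (30 per arm, r_pre 0.3, r_rand 0.8) over the planned Kruskal-Wallis test. For the CMH test the gain was about 2 to 12 points (50% to 52-62%). All of these depend on assumed correlations, item distributions and effect sizes, and the larger gains need the Randomization value to be clearly more prognostic than recalled pre-fracture status. That is plausible but undocumented.

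A single multiplier for the variance lost should not be quoted. For example, the variance of change from pre-fracture relative to simple change from Randomization, at r_pre 0.4 and r_rand 0.5, is (1 − 0.4)/(1 − 0.5) = 1.2 with equal SDs. It becomes (1 + 0.25 − 0.4)/(2 × 0.5) = 0.85 if the pre-fracture SD is half the later SD, so the direction itself reverses.

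**What to change.** Amend SAP 2.10.3.2.1 before any ADL results by treatment group are produced:

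1. Keep the change-from-screening analyses, labelled as the description of recovery to pre-fracture status.
2. At post-baseline visits, stratify the between-arm CMH test by dependence at Randomization (yes/no), item by item.
3. For item scores, base the between-arm test on a rank or ordinal model adjusted for the Randomization post-fracture value and country. Do not substitute a simple change from Randomization.

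The model in step 3 needs a stated ordering of the response codes. In Appendix 15.7, the physical-item codes for activities not performed for non-health reasons, do not know and refused are not degrees of dependence. The planned Kruskal-Wallis test needs the same rule.

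The data are already collected, so the cost is programming and one more set of exploratory tables. For items where few subjects are dependent, some strata will be sparse and stratification will add little.

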9.3.2 Physical Performance Assessments

The 6MWT total distance walked will be analyzed using an Analysis of Covariance model with baseline value as a covariate and treatment as a primary factor. Observed values, change from baseline and placebo adjusted change from baseline will be summarized using mean, standard deviation, coefficient of variation (CV%), median, minimum and maximum.

Grip strength will be analyzed using an Analysis of Covariance model with baseline value as a covariate and treatment as a primary factor. Observed values, change from baseline and placebo adjusted change from baseline will be summarized using mean, standard deviation, coefficient of variation (CV%), median, minimum and maximum.

SPPB score will be summarized using frequency counts. Observed values and change from baseline will be summarized. A Kruskal-Wallis test (ANOVA on ranks) will be used to test for differences between treatment groups.

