1.2. Study Overview

This is a phase II, randomized, double-blind, parallel group, placebo-controlled, multi-center study to investigate the safety, tolerability, and efficacy of VK5211 after 12 weeks of treatment.

Males and females \geq 65 years old who are ambulatory and recovering from a hip fracture will be eligible for participation 3-11 weeks post-injury.

After completing all Screening requirements, subjects will be randomized to one of four treatment arms (VK5211 0.5 mg, 1.0 mg, 2.0 mg, or placebo) in a 1:1:1:1 ratio and will receive their first dose of study treatment in the clinic.

The first bottle of study treatment will be dispensed and subjects will be instructed to take one oral dose of the assigned treatment at approximately the same time every morning, 30 minutes prior to breakfast.

Subjects will undergo safety and efficacy assessments as specified in the protocol on an approximately 4-week basis for a total treatment period of approximately 12 weeks. Following the 12-week treatment period, subjects will be followed for an additional 12-week period for assessment of safety and duration of drug effect.

During the study safety will be assessed on an ongoing basis by adverse events, identification of dose-limiting toxicities (DLTs) (if any), plasma concentrations, general physical examinations, vital signs, clinical laboratory assessments in blood, urine, as well as other specialized testing as required.

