1.3.3. Exploratory Objectives

The exploratory objectives of this study are to determine the efficacy of VK5211 compared to placebo after 12 weeks of treatment by:

- Physical Performance Assessments
 - 6 Minute Walk Test (6MWT) and BORG Scale
 - Grip Strength
 - Short Physical Performance Battery (SPPB)
- Patient Reported Outcomes
 - Pre- and Post-fracture Physical and Instrumental Activities of Daily Living (PADLs/IADLs)
 - Short Form-36 (SF-36)

2. Detailed Statistical Methods

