2.10.3.1.3. Short Physical Performance Battery

SPPB individual scores and total scores will be summarized using frequency counts and summary statistics. Observed values and change from baseline will be summarized.

Number and percent of subjects that:

- Improved by at least 1, 2 and 3 points,
- Whose total score is greater than 7, and
- Whose 4-meter gait speed increased by more than 0.1 m/sec

will be presented.

A Cochran-Mantel-Haenszel row mean score will be used to test for differences in frequency counts between treatment groups. An Analysis of Covariance with base value as a covariate and country as factor will be used to test for differences in the mean.

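### The exploratory daily-living objective is VK5211 versus placebo, but the planned between-arm tests for the PADLs/IADLs contain no placebo contrast and no effect estimate

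*SAP*

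**What the plan says.** - **Objective (SAP 1.3.3; Protocol 3.2).** The exploratory aim is to "determine the efficacy of VK5211 compared to placebo after 12 weeks of treatment by" a list of measures that includes the SPPB and the pre- and post-fracture PADLs/IADLs.
- **Design (SAP 1.2).** There are four arms: "subjects will be randomized to one of four treatment arms (VK5211 0.5 mg, 1.0 mg, 2.0 mg, or placebo) in a 1:1:1:1 ratio".
- **PADL/IADL change (SAP 2.10.3.2.1; same in Protocol 9.3.3).** "Differences between treatment groups for each activity of daily living will be analyzed using the Kruskal-Wallis test", applied to each subject's change since screening.
- **PADL/IADL dependence (same sections).** The number of entirely dependent subjects "at each visit between treatment groups will be compared using the Cochran-Mantel-Haenszel Test". The remaining two tests in the section, a CMH test and a signed-rank test on change from screening, concern change over time rather than a comparison of arms.
- **SPPB (SAP 2.10.3.1.3).** "A Cochran-Mantel-Haenszel row mean score will be used to test for differences in frequency counts between treatment groups". A separate ANCOVA tests the mean; its sentence names the baseline value and country but not treatment.
- **Contrast with other endpoints.** For the DXA measures and bone turnover markers the SAP reports a placebo-adjusted change with a 95% CI (2.10.1, 2.10.2.1). For grip strength it reports a placebo-adjusted change (2.10.3.1.2). Nothing equivalent is written for the PADLs/IADLs.

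**The concern.** The objective and the test ask different questions. The objective asks whether VK5211 differs from placebo. A four-group rank test asks whether any arm differs from any other. It can reject because two doses differ from each other, or because a dose does worse than placebo, and the p-value looks the same in each case. With no placebo contrast, pairwise follow-up, trend test or estimate written down for the PADLs/IADLs, the plan gives no test or interval for the stated question. Any placebo comparison would then have to be chosen after the treatment codes are known.

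A second question is whether the omnibus test also costs power compared with a direct placebo contrast.

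**Working it through.** **1. The plan's own power figures are placebo pairs.** SAP 2.14 gives differences of 1.0 kg (1 mg) and 1.5 kg (2 mg), SD 1.3 and 30 per arm. Alpha is not stated there; two-sided 0.05 is assumed throughout.
- Standard error = 1.3 × √(2/30) = 0.336.
- 1 mg: 1.0/0.336 = 2.98; Φ(2.98 − 1.96) = 0.846. Noncentral t gives 0.834. The plan says 84%.
- 2 mg: 1.5/0.336 = 4.47; Φ(4.47 − 1.96) = 0.994. Noncentral t gives 0.993. The plan says 99%.

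The figures reproduce, and both are dose-versus-placebo comparisons. The PADL/IADL tests are not of that form.

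**2. Can a significant four-group result fail to involve placebo?** This was simulated as Kruskal-Wallis against unadjusted Wilcoxon placebo pairs (2,000 runs, normal data, Monte Carlo error about 1 point).
- *One dose 0.5 SD above placebo, one 0.5 SD below, the third equal to it (illustrative only).* Kruskal-Wallis is significant in 78% of trials at 23 per arm. In 18% of those, no placebo pair reaches p<0.05. At 30 per arm the figures are 90% and 14%.
- *The plan's ordered lean-mass pattern.* This happens in 0.5% or less. At half that effect it happens in about 4 to 6%.

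**3. Power under the plan's dose order.** The documents give no effect size for any daily-living item, so one has to be assumed. Take the pre-study pattern 0 / 0.5 / 1.0 / 1.5 and halve it: d = 0.5 × 1.5/1.3 = 0.577 SD for 2 mg, so d² = 0.333.
- Two arms: noncentrality = n·d²/2, on 1 and 2n−2 df.
- Four arms with means 0, d/3, 2d/3, d: the squared deviations sum to (1/4 + 1/36 + 1/36 + 1/4)d² = 0.556d², so noncentrality = 0.556·n·d², on 3 and 4n−4 df.
- At n = 23: 23 × 0.333/2 = 3.83 and 0.556 × 23 × 0.333 = 4.25.

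| n per arm | 2 mg effect | Four-group test | 2 mg vs placebo |
|---|---|---|---|
| 23 | 0.58 SD | 36% | 48% |
| 26 | 0.58 SD | 41% | 53% |
| 30 | 0.58 SD | 47% | 59% |
| 26 | 0.80 SD | 71% | 81% |
| 23 | 1.15 SD (full lean-mass effect) | 94% | 97% |
| 30 | 1.15 SD | 98% | 99% |

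A binary dependence outcome with assumed rates of 50/40/30/20% gives a similar gap: 45% against 58% at 23 per arm, and 57% against 69% at 30.

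**4. Where the loss disappears (simulation).**
- *Half effect, ordered.* Three Bonferroni-adjusted placebo pairs (at least one significant) have the same power as Kruskal-Wallis: 33% each at 23 per arm, 44% each at 30.
- *Only 2 mg works, 0.75 SD, 23 per arm.* Kruskal-Wallis 71%, the single 2 mg pair 70%, Bonferroni pairs 52%.

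**The case against.** The best reply has five parts.

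1. **Power.** A reader might infer that the four-group test simply wastes power. The documents do not support that. The gap needs an assumed moderate effect, an ordered dose response and a single unadjusted comparator. Under other reasonable settings it is nil or reversed. The calculations also use mostly normal data, while the items are coded categories. This part stands.
2. **SPPB.** A reader might infer that the SPPB has the same gap. It does not, quite: an ANCOVA on the mean and responder counts are also planned. The Kruskal-Wallis test in Protocol 9.3.2 ("A Kruskal-Wallis test (ANOVA on ranks) will be used to test for differences between treatment groups") is replaced in the SAP. This stands in part, because the ANCOVA sentence lists neither treatment nor a placebo difference.
3. **The CMH wording.** The sentences do not say how many groups enter the test. Four is the natural reading but is not fixed by the text. The table shells are in a separate file (SAP 4.3) that is not available, so pairwise columns cannot be ruled out. This stands as a limit on certainty, but the comparison should still be written in the SAP.
4. **By-arm summaries.** Means, medians and counts by arm (SAP 2.1, 2.10.3.2.1) will show direction informally. That is true, but they supply neither a test nor an interval against placebo.
5. **Consequence.** The endpoints are exploratory, and the PADLs/IADLs are not in the primary analysis list of SAP 2.11. This limits the importance; it does not remove the mismatch.

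**Conclusion.** The mismatch for the PADLs/IADLs is real. The objective names placebo, and no visible text turns the between-arm tests into a comparison with placebo or gives an estimate. A significant Kruskal-Wallis result would leave open which dose differs from placebo, and in which direction. If the effect follows the plan's assumed order at full size, a significant result that involves no placebo pair is rare, so the main loss is of a stated answer rather than a high chance of a misleading one.

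The power argument is conditional. At 23 to 30 per arm the four-group test gives up about 12 points to a single 2 mg versus placebo contrast at an assumed 0.58 SD, and 1 to 3 points at the full lean-mass effect. It gives up nothing to Bonferroni-adjusted pairs under the ordered pattern, or to the 2 mg pair if only the top dose works. A general claim of lost power, or a claim that the SPPB has no other analysis, would go beyond the documents. Because the endpoints are exploratory, this is a minor but worthwhile correction.

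**What to change.** **PADLs/IADLs (SAP 2.10.3.2.1).** At the 12-week visit named in the objective, add each dose versus placebo:
- Wilcoxon rank-sum for ordinal change from screening;
- a two-arm CMH test for dependent or not dependent, with the CMH statistic named;
- for each, an estimated difference with a 95% CI as the main output.

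Label the p-values exploratory and unadjusted across items, and keep the four-group test as supportive. A fixed testing order is not needed. It would stop at the first failure, while Protocol 5.3 wants information on the minimal effective dose.

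**SPPB (SAP 2.10.3.1.3).** List treatment in the ANCOVA and report dose-minus-placebo differences with 95% CIs.

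**Cost.** SAP wording and some table columns, with no new data or subjects. The downside is more exploratory p-values. With 16 PADL and 4 IADL items there are 20 × 3 = 60 placebo comparisons per test at 12 weeks, instead of 20 four-group ones. For scale, the plan already implies about 20 × 5 = 100 between-arm CMH tests across the five post-screening visits. Restricting the new comparisons to 12 weeks and leading with intervals keeps this manageable.
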